# A.5. Tolerability of LDX for the treatment of severe obesity in children is unknown

Although psychostimulants, including LDX, have a long-standing, well-established safety profile,  the relative tolerability of these medications in children who do not have ADHD has yet to be established. Aside from decreased appetite, the most common side effects of psychostimulants in children with ADHD include insomnia, upper abdominal pain, and irritability. Particularly relevant to patients with obesity are the impact of psychostimulants on blood pressure, heart rate and linear growth, the effects of which tend to be dose dependent in children with ADHD.  Clinical trials of LDX for the treatment of ADHD in children report

PROTOCOL TITLE: Lisdexamfetamine for the Treatment of Severe Obesity in Children Aged

6 to 12 Years

VERSION DATE: 19Sep2025

[figure not shown]
mean increases in systolic blood pressure of 2-4 mm Hg and in heart rate of 3-7 bpm. The clinical significance of this effect on the cardiovascular system is uncertain, especially for children with obesity who may be at higher risk of having underlying cardiovascular impairment such as hypertension. Importantly, in adults with obesity treated with phentermine, also a noradrenergic agent, blood pressure tends to decrease as a function of weight loss. 12 Thus, measuring the impact of LDX on blood pressure and heart rate in children with obesity is critical for assessing its utility as an adjunct treatment for obesity in this population. Regarding linear growth, psychostimulants have been shown to have adverse effects on height velocity at various stages of childhood, including prepuberty. 13,14 However, final adult height does not appear to be impacted. 15 Similarly, obesity can effect growth and has been associated with taller stature during childhood but decreased growth velocity in adolescence; the net result again is no association between childhood weight status and adult height. 16 That said, as both psychostimulant use and obesity can affect growth velocities during the pre- and peri-pubertal periods, the net effect of both of these simultaneously during this stage of development is unclear and warrants further investigation.

2.2 Preliminary Data: To our knowledge, no randomized controlled trials have examined psychostimulants as an adjunct to lifestyle therapy for BMI reduction in children with obesity. At the University of Minnesota Pediatric Weight Management Clinic, where off-label use of medications for the treatment of obesity is guided by protocols developed by our team of pediatric obesity medicine physicians, we have used LDX as an adjunct to lifestyle therapy for the treatment of obesity in patients. We identified 65 patients, ≥6 years of age with severe obesity, who were treated with LDX plus our standard of care lifestyle therapy for at least 3 months. The mean absolute change in the percent of the 95th BMI percentile (%BMIp95) was -4.68 and -6.35 percentage points at 3- and 6-months, respectively (see Figure 2). In a sub-analysis including only patients ages > 6 to < 12 years (n=37), the mean absolute change in %BMIp95 was -5.94 and -8.41 percentage points at 3- and 6-months, respectively.

PROTOCOL TITLE: Lisdexamfetamine for the Treatment of Severe Obesity in Children Aged

6 to 12 Years

VERSION DATE: 19Sep2025

2.3 Existing Literature: Several case series and retrospective medical chart reviews describe the results of treating hypothalamic obesity (most often from brain tumors) in children with psychostimulants. These reports demonstrated BMI stabilization or reduction with dextroamphetamine or methylphenidate. A case series of children with monogenic obesity due to mutations in leptin receptor or melanocortin-4 receptor also demonstrated favorable BMI outcomes with methylphenidate treatment.

### 3.0 Study Endpoints/Events/Outcomes

- 3.1 Primary Endpoint/Event/Outcome: To estimate the treatment effect of LDX + lifestyle therapy vs. placebo + lifestyle therapy on changes in BMI (%BMIp95), body fat, cardiometabolic health and quality of life (QOL) from baseline to 24 weeks. We hypothesize that LDX compared to placebo will result in a greater mean decrease in %BMIp95 and body fat, improved cardiometabolic health and QOL at 24 weeks.
- 3.2 Secondary Endpoint(s)/Event(s)/Outcome(s): To generate estimates of the tolerability and safety of LDX used for the treatment of severe obesity in children. We hypothesize that at least 80% of participants will tolerate an LDX dose of at least 30 mg per day (the recommended starting dose) and that the LDX group compared to the placebo group will not demonstrate clinically significant increases in blood pressure or heart rate.

PROTOCOL TITLE: Lisdexamfetamine for the Treatment of Severe Obesity in Children Aged

6 to 12 Years

VERSION DATE: 19Sep2025

We will also examine the potential mechanisms by which LDX affects BMI in children with obesity, including its effect on executive functioning, reward processing, appetite, resting energy expenditure, and health behaviors (diet, eating behaviors, and physical activity). Study Intervention(s)/Investigational Agent(s)

#### 3.3 Description:

LDX: LDX, a psychostimulant prodrug of dextroamphetamine, is FDA-approved for ADHD in children ≥6 years of age and for binge eating disorder in adults. It is available in capsules of 10, 20, 30, 40, 50, 60, and 70 mg. It is orally administered once daily and has a half-life of 12 hours. After a single dose, the pharmacokinetics are linear between 30 and 70 mg in children ages 6-12 years, and both the clinical efficacy for ADHD symptoms and weight loss side effects are dose dependent. Following single doses of 30 mg to 70 mg, the weight/dose normalized area under the curve and maximal concentration values are the same in 6-12 year olds compared to adults. Per the package insert, the recommended starting dose for children ≥6 years of age with ADHD is 30 mg daily. The dose is adjusted by 10 or 20 mg increments at weekly intervals up to a maximum of 70 mg daily. The target dose is one that balances the clinical efficacy with tolerability. For binge eating disorder in adults, the recommended dose is 50-70 mg daily. To operate conservatively and allow for maximum tolerability, we will start at 30 mg daily for 2 weeks, then 40 mg daily for 2 weeks, then 50 mg daily for 2 weeks, then 60 mg daily for 2 weeks, then 70 mg daily for the remaining 14 weeks. We will not use a forced titration schedule. That is, for patients who do not tolerate the full dose escalation schedule, we will maintain the dose at the maximum tolerated dose for the remainder of the trial. Also, we will not escalate the dose after week 10, which is the end of the planned dose escalation schedule. A participant's dose may be decreased for medication intolerance anytime during the trial; the dose will be reduced by 10 mg at weekly intervals until a tolerable dose is achieved. If a participant cannot tolerate the smallest dose, 10 mg, then drug/placebo will be discontinued but the participant will remain in the trial. This flexible dosing will allow for maximal time on medication. Placebo capsules that are identical in appearance to the LDX capsules will be made by the University of Minnesota Investigational Drug Service Pharmacy, which will manage all trial product.

Lifestyle Therapy: Lifestyle therapy will focus on dietary and physical activity modification supported by behavior change strategies. The standardized curriculum will be based on a behavioral conceptualization of effective weight management that emphasizes: 1) identifying behaviors in need of change; 2) setting goals for change; 3) monitoring progress; 4) modifying environmental cues to facilitate change; and 5) modifying consequences to motivate change (e.g. positive reinforcement for goal attainment). Each session will be delivered by an

PROTOCOL TITLE: Lisdexamfetamine for the Treatment of Severe Obesity in Children Aged

6 to 12 Years

VERSION DATE: 19Sep2025

RD-trained research coordinator, who will follow a standardized format including a review of progress, new material, and a summary/plan for the upcoming session. A total of 13 sessions, each 30-60 minutes in length, will be delivered every 2 weeks, 7 in-person and 6 virtually (delivered by a secure virtual platform). Virtual visits may be conducted with the parent/guardian alone (without participant present) to allow for more flexibility in scheduling and to minimize time away from school.

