# 1.0 Objectives

1.1 Purpose: This will be a single site, 24-week double-blind, randomized, placebocontrolled pilot and feasibility clinical trial designed to estimate the treatment effect and tolerability of lisdexamfetamine (Vyvanse™) for the treatment of severe obesity in children ages 6 to < 12 years. After careful screening, all eligible participants (n=44) will be randomized, 1:1, to either lisdexamfetamine plus lifestyle therapy or placebo plus lifestyle therapy for 24 weeks of intervention. Participants and their parent/guardian will attend 8 in-person and 6 virtual visits. Participants will undergo regular assessments of anthropometrics, blood pressure, heart rate, and side effects and interval assessments of body composition, bone age, Tanner stage, laboratory tests, and questionnaires.

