| VAS of Hunger                                  |             |                                                 |                    |                    |                    |                    |                     |                     |                     |              |                     |                     |                     |                     |
| • CBES                                         |             |                                                 |                    |                    |                    |                    |                     |                     |                     |              |                     |                     |                     |                     |
| • BIS/BAS                          |             |                                                 |                    |                    |                    |                    |                     |                     |                     |              |                     |                     |                     |                     |
| Planned dose escalation (mg)                   |             | 30                                              | 40                 | 50                 | 60                 | 70                 |                     |                     |                     |              |                     |                     |                     |                     |
| Dispense study medication                      |             | X                                               |                    | X                  | - 00               | X                  |                     | X                   |                     | X            |                     | X                   |                     |                     |
| Compliance check                               |             |                                                 | Х                  | X                  | Х                  | X                  | Х                   | X                   | X                   | X            | X                   | X                   | Х                   | X                   |

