- Lifestyle therapy. Lifestyle therapy will focus on dietary and physical activity modification supported by behavior change strategies. The standardized curriculum will be based on a behavioral conceptualization of effective weight management that emphasizes: 1) identifying behaviors in need of change; 2) setting goals for change; 3) monitoring progress; 4) modifying environmental cues to facilitate change; and 5) modifying consequences to motivate change (e.g., positive reinforcement for goal attainment). Each session will be delivered by an RD-trained research coordinator, who will follow a standardized format including a review of progress, new material, and a summary/plan for the upcoming session. A total of 13 sessions, each 30-60 minutes in length, will be delivered every 2 weeks, 7 in-person and 6 virtually (delivered by a secure virtual platform). Virtual visits may be conducted with the parent/guardian alone (without participant present) to allow for more flexibility in scheduling and to minimize time away from school.
- 4.3 Study Duration: Individuals will be enrolled in the study for up to 27 weeks, including 24 weeks of intervention and up to 3 weeks between screening and start of intervention.

We anticipate that it will take 2.5 years to recruit and enroll the 44 participants needed for this pilot trial and that data collection will be completed after 3.5 years. We anticipate it will take 1 year to analyze the data.

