#### Week 2 (virtual visit):

- Compliance check
- Review adverse events, concomitant medications, intercurrent illness and Barkley Side Effect Rating Scale
- Dose escalation (if tolerated)
- Virtual lifestyle therapy visit

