### Week 4 (in person visit):

- Height, weight, blood pressure and heart rate
- Urine pregnancy test
- Suicide and depression screening (C-SSRS and CDI-2)
- Compliance check and return unused study medication
- Review adverse events, concomitant medications, intercurrent illness and Barkley Side Effect Rating Scale
- Dose escalation (if tolerated) and study drug dispensing
- In-person lifestyle therapy visit

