#### Week 10 (virtual visit):

- Compliance check
- Review adverse events, concomitant medications, intercurrent illness and Barkley Side Effect Rating Scale
- Virtual lifestyle therapy visit

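### Do the dose steps in section 3.3, which add up to 22 weeks, call for a change to a 24-week trial?

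*Combined protocol and SAP*

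**What the plan says.** The intervention length is stated consistently. Section 1.1 gives "placebo plus lifestyle therapy for 24 weeks of intervention", and section 4.3 describes total participation as "including 24 weeks of intervention and up to 3 weeks between screening and start of intervention".

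Section 3.3 lists five dose levels. The first three (30, 40 and 50 mg) last two weeks each, "then 60 mg daily for 2 weeks, then 70 mg daily for the remaining 14 weeks". It adds that "we will not escalate the dose after week 10, which is the end of the planned dose escalation schedule".

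Other places bear on the same timetable:

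- The planned-dose row of the schedule of events (section 4.1) has 30 at baseline, 40 at week 2, 50 at week 4, 60 at week 6 and 70 at week 8. It is blank from week 10 on.
- The visit lists in section 7.3 include an escalation item at weeks 2, 4, 6 and 8 (at weeks 4 and 8: "Dose escalation (if tolerated) and study drug dispensing") and none at week 10.
- Footnote 4 of the schedule, on the side-effect rating scale, describes dose escalation as lasting through week 10.

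**The concern.** In 3.3 the last duration is given as what remains of the trial, so the five durations should total 24 weeks. They do not. Read literally, 3.3 accounts for dosing only up to week 22 and leaves two weeks without a stated dose.

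The week 10 statement looks like a second fault. By 3.3's own step lengths the fourth and last planned increase falls at week 8, and the week 10 visit list has no escalation item. That visit being virtual does not explain the absence, because the virtual visits at weeks 2 and 6 do list one.

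If the text really meant a 22-week course, or if sites could not tell when the last level begins, exposure at the highest level would be uncertain in a trial whose primary endpoint is read at week 24. Section 12.1 also allows escalation to be halted while an ambulatory blood pressure result is awaited, so a reader may ask whether a step that was held and then released can be taken at week 10.

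**Working it through.** **Inputs.** Intervention length: 24 weeks (1.1, 4.3). Step durations: 2, 2, 2, 2 and 14 weeks (3.3). Start of each level: baseline and weeks 2, 4, 6 and 8 (planned-dose row, 4.1; escalation items, 7.3). Stated end of escalation: week 10 (3.3; footnote 4).

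**The plan's own figure.** Fourteen weeks is reproduced only by counting from week 10: 24 − 10 = 14.

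**Adding the steps as written.**

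| Level (mg) | Stated weeks | Start (week) | End (week) |
|---|---|---|---|
| 30 | 2 | 0 | 2 |
| 40 | 2 | 2 | 4 |
| 50 | 2 | 4 | 6 |
| 60 | 2 | 6 | 8 |
| 70 | 14 | 8 | 22 |

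Total = 2 + 2 + 2 + 2 + 14 = 22. Shortfall = 24 − 22 = 2 weeks. Remaining from week 8 = 24 − 8 = 16 weeks, against 14 stated.

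**Can 14 and week 10 be explained together?** Five levels at two weeks each take 5 × 2 = 10 weeks, and 24 − 10 = 14. If the first two weeks at the last level are counted as part of escalation, the week 10 statement, footnote 4 and the figure 14 all agree. The sentence in 3.3 would then have merged two periods at the last level: 2 + 14 = 16 weeks. This reading is an inference, since 3.3 does not state a fifth two-week step. It does show that one compressed sentence could account for both oddities.

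**Is week 10 in conflict with week 8?** No. A rule against increases after week 10 is an outer limit, and a last planned increase at week 8 falls within it.

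**Is treatment planned to stop at week 22?** No. The schedule dispenses drug at week 20, the next in-person visit is week 24, compliance is checked and unused drug returned at week 24, and section 4.2 (resting energy expenditure) has participants take study medication on the morning of that visit.

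**Does any analysis use the figure 14 or the week 10 limit?**

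- The primary outcome (section 14) is change in %BMIp95 from baseline to week 24, compared between randomised groups with baseline adjustment. Planned weeks at a level do not enter.
- The tolerability criterion (Aim 2) turns on 30 mg over 24 weeks, not on time at the highest level.
- The imputation model in 14.1 includes LDX dose, which is not a planned number of weeks.
- Section 14 says the sample size was not set by a power calculation, so no such figure is affected.

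**The case for a change.** The strongest case for a change is that dosing text should be correct in its own right. Staff may work from 3.3 as well as from the visit lists, and a protocol should not need a second passage to repair the first. The held step is the most concrete example. Assume a first raised blood pressure at week 4 and two confirmations at two-week intervals (the spacing is an assumption). That reaches week 4 + 2 + 2 = 8 with the monitor result pending. Section 3.3 does not bar an increase at week 10, yet the week 10 list has no escalation item, and dispensing is scheduled at weeks 8 and 12 but not 10. The rule in 3.3 about staying at the highest tolerated level addresses intolerance, not a step that was held and then cleared.

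The sum stands without qualification: 22 is not 24. The held-step point stands only as an unstated detail. Section 3.3 rules out increases after week 10, and the week 10 list follows the planned sequence, in which the last level has already begun. Absence of a routine item there does not prohibit a delayed step. The documents give no frequency for such holds and nothing suggests they would tend to clear at week 10. This review takes no position on what should happen in that case.

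**Conclusion.** This is a clerical slip. The durations in 3.3 fall two weeks short (22 against 24; 14 against 16 for the last step). The week 10 statement is not a separate contradiction, and it may well have the same origin as the figure 14.

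No change to design, conduct or analysis follows. The planned start of each level is the same in the schedule row, the visit lists and 3.3's own step lengths, and drug supply and compliance checks run to the end of the 24 weeks. The shown effect on drug received, on the primary comparison and on the 30 mg criterion is nil.

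This rests on two assumptions: that staff use the schedule and visit lists to time the steps, and that dispensing proceeds as scheduled. Section 3.3, the schedule row, footnote 4 and the week 8 and week 10 lists must be reconciled as an editorial matter, and which wording is right is for the investigators to say.

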# 3.4 Drug/Device Handling:

LDX will be purchased commercially. The University of Minnesota Investigational Drug Service (IDS) Pharmacy will be asked to prepare a matching placebo. Trial product will be managed by IDS and will be dispensed according to their operating policies. The IDS office specializes in storing and dispensing investigational drugs for clinical trials. Study physicians will write a prescription in order for IDS to dispense the study medication. IDS is a secure facility (behind two locked doors) and maintains refrigerators and freezers with temperature tracking to assure that the drugs utilized in this study will maintain stability. IDS will keep detailed records on the receipt of investigational product (including lot numbers) and detailed records on the dispensing of the product to each subject enrolled in the study. IDS is also equipped to destroy any medication that is returned at the end of the study when all drug accountability has been completed. The participants and their parents will be instructed on how to administer the medication and the dose escalation. Study staff members will perform drug accountability at each visit and estimate a percentage of missed doses as additional forms of compliance tracking.

3.5 Biosafety: Not applicable.

3.6 Stem Cells: Not applicable.

3.7 Fetal Tissue: Not applicable.

### 4.0 Procedures Involved

4.1 Study Design: This will be a 24-week, randomized, double-blind, placebo-controlled pilot and feasibility clinical trial of LDX plus lifestyle therapy versus matching placebo plus lifestyle therapy. We will enroll 44 children who have previously failed to lose weight with lifestyle therapy per parent report.

PROTOCOL TITLE: Lisdexamfetamine for the Treatment of Severe Obesity in Children Aged

6 to 12 Years

VERSION DATE: 19Sep2025

[figure not shown]

Figure 3. Clinical Trial Framework

The schedule of events shows the data that will be collected at each study visit. All participants will receive reimbursement for completing study visit assessments.

PROTOCOL TITLE: Lisdexamfetamine for the Treatment of Severe Obesity in Children Aged

6 to 12 Years

VERSION DATE: 19Sep2025

| SION DATE. 1936p2023                           |             |                                                 |                    |                    |                    |                    |                     |                     |                     |              |                     |                     |                     |                     |
|------------------------------------------------|-------------|-------------------------------------------------|--------------------|--------------------|--------------------|--------------------|---------------------|---------------------|---------------------|--------------|---------------------|---------------------|---------------------|---------------------|
|                                                | X Screening | Baseline/
Randomization
+21d  | Week 2 ± 3d | Week 4 + 3d | Week 6 + 3d | Week 8 ± 3d | Week 10 + 3d | Week 12 + 7d | Week 14 + 7d | Week 16 ± 7d | Week 18 + 7d | Week 20 + 7d | Week 22 + 7d | Week 24 + 7d |
| Informed Consent                               | X           |                                                 |                    |                    |                    |                    |                     |                     |                     |              |                     |                     |                     |                     |
| Inclusion/Exclusion                | X           |                                                 |                    |                    |                    |                    |                     |                     |                     |              |                     |                     |                     |                     |
| Demographics                                   | X           |                                                 |                    |                    |                    |                    |                     |                     |                     |              |                     |                     |                     |                     |
| Medical history, including chemical dependency | X           |                                                 |                    |                    |                    |                    |                     |                     |                     |              |                     |                     |                     |                     |
| Height, weight, blood pressure and heart rate  | X           | X                                               |                    | X                  |                    | X                  |                     | X                   |                     | X            |                     | X                   |                     | X                   |
| Physical exam                                  | X           | Λ                                               |                    | Λ                  |                    | Λ                  |                     | Λ                   |                     | Λ            |                     | Λ                   |                     | Λ                   |
| Tanner stage                                   | X           |                                                 |                    |                    |                    |                    |                     |                     |                     |              |                     |                     |                     | X                   |
| ECG ECG                                        | X           |                                                 |                    |                    |                    |                    |                     |                     |                     |              |                     |                     |                     | Λ                   |
| Basic metabolic panel  , TSH       | X           |                                                 |                    |                    |                    |                    |                     |                     |                     |              |                     |                     |                     |                     |
| Pregnancy test                     | X           | X                                               |                    | X                  |                    | X                  |                     | X                   |                     | X            |                     | X                   |                     | X                   |
| Suicide and Depression Screen                  | Λ           | Λ                                               |                    | Λ                  |                    | Λ                  |                     | Λ                   |                     | Λ            |                     | Λ                   |                     | Λ                   |
| C-SSRS                                         | Х           | X                                               |                    | Х                  |                    | Х                  |                     | Х                   |                     | Х            |                     | Х                   |                     | Х                   |
| • CDI-2                                        | Λ           | Λ                                               |                    | Λ                  |                    | Λ                  |                     | Λ                   |                     | Λ            |                     | Λ                   |                     | Λ                   |
| Bone age                                       |             | X                                               |                    |                    |                    |                    |                     |                     |                     |              |                     |                     |                     | X                   |
| Indirect calorimetry                           |             | X                                               |                    |                    |                    |                    |                     |                     |                     |              |                     |                     |                     | X                   |
| Fasting blood tests                            |             | Λ                                               |                    |                    |                    |                    |                     |                     |                     |              |                     |                     |                     | Λ                   |
| • Lipids                                       |             |                                                 |                    |                    |                    |                    |                     |                     |                     |              |                     |                     |                     |                     |
| • Glucose                                      |             |                                                 |                    |                    |                    |                    |                     |                     |                     |              |                     |                     |                     |                     |
| • Insulin                                      | X           |                                                 |                    |                    |                    |                    |                     |                     |                     |              |                     |                     |                     | Х                   |
| • HbA1c                                        | Λ           |                                                 |                    |                    |                    |                    |                     |                     |                     |              |                     |                     |                     | ^                   |
| • AST                                          |             |                                                 |                    |                    |                    |                    |                     |                     |                     |              |                     |                     |                     |                     |
| • ALT                                          |             |                                                 |                    |                    |                    |                    |                     |                     |                     |              |                     |                     |                     |                     |
| DXA                                            |             | X                                               |                    |                    |                    |                    |                     |                     |                     |              |                     |                     |                     | X                   |
| Diet recall                                    | X           | X                                               |                    |                    |                    |                    |                     |                     |                     |              |                     |                     | X                   | X                   |
| Accelerometry                      | X           | Λ                                               |                    |                    |                    |                    |                     |                     |                     |              |                     | X                   | Λ                   | Λ                   |
| Questionnaires                                 | Λ           |                                                 |                    |                    |                    |                    |                     |                     |                     |              |                     | Λ                   |                     |                     |
| • Peds QL                                      |             |                                                 |                    |                    |                    |                    |                     |                     |                     |              |                     |                     |                     |                     |
| NIH Toolbox                                    |             |                                                 |                    |                    |                    |                    |                     |                     |                     |              |                     |                     |                     |                     |
| • BRIEF-2                                      |             |                                                 |                    |                    |                    |                    |                     |                     |                     |              |                     |                     |                     |                     |
| NICHQ-Vanderbilt                               |             | X                                               |                    |                    |                    |                    |                     |                     |                     |              |                     |                     |                     | Х                   |
| • CEBQ                                         |             |                                                 |                    |                    |                    |                    |                     |                     |                     |              |                     |                     |                     | 11                  |
| VAS of Hunger                                  |             |                                                 |                    |                    |                    |                    |                     |                     |                     |              |                     |                     |                     |                     |
| • CBES                                         |             |                                                 |                    |                    |                    |                    |                     |                     |                     |              |                     |                     |                     |                     |
| • BIS/BAS                          |             |                                                 |                    |                    |                    |                    |                     |                     |                     |              |                     |                     |                     |                     |
| Planned dose escalation (mg)                   |             | 30                                              | 40                 | 50                 | 60                 | 70                 |                     |                     |                     |              |                     |                     |                     |                     |
| Dispense study medication                      |             | X                                               |                    | X                  | - 00               | X                  |                     | X                   |                     | X            |                     | X                   |                     |                     |
| Compliance check                               |             |                                                 | Х                  | X                  | Х                  | X                  | Х                   | X                   | X                   | X            | X                   | X                   | Х                   | X                   |
| AE Review                                      |             |                                                 |                    |                    |                    |                    |                     |                     |                     |              |                     |                     |                     |                     |
| • AEs                                          |             |                                                 |                    |                    |                    |                    |                     |                     |                     |              |                     |                     |                     |                     |
| Barkley Rating Scale               |             | X                                               | Х                  | X                  | X                  | X                  | Х                   | Х                   | X                   | Х            | X                   | X                   | Х                   | Х                   |
| • Con Meds                                     |             |                                                 |                    |                    | -                  |                    | -                   |                     | -                   |              | -                   |                     | _                   |                     |
| Intercurrent Illness                           |             |                                                 |                    |                    |                    |                    |                     |                     |                     |              |                     |                     |                     |                     |
| Lifestyle therapy (in-person)                  |             | X                                               |                    | X                  |                    | X                  |                     | X                   |                     | X            |                     | X                   |                     | X                   |
